9.1 Adverse Events

All reported AEs will be classified by system organ class (SOC), preferred term, and lower-level term using MedDRA Version 23.1 or later.

All reported AEs with start date on or after the first exposure to IMP until the end of the study (including Taper and Follow-up period) will be analyzed.

All AEs will be listed. Listings will include the start and stop day of the AE, severity (Mild, Moderate, Severe) relationship to IMP (Yes, No), whether serious (Yes/No) and if serious, SAE

criteria, Action Taken with respect to IMP (Not Applicable, Dose Not Changed, Dose Reduced, Drug Interrupted, Drug Withdrawn, Dose Increased, or Unknown), whether participant received Treatment and if yes, treatment received, AE Outcome (Fatal, Not Recovered/Not Resolved, Resolved/Recovered, Recovered/Resolved with Sequela, Recovering/Resolving), and whether AE caused participant to discontinue from study (Yes/No). Partially or completely missing AE start and end dates will not be imputed.

9.2 Clinical Laboratory Evaluation

9.2.1 Hematology and Biochemistry

Hematology and Biochemistry results will be listed for all participants in the safety analysis set.

If values for any of the parameters are below or above the limit of quantification of the assay (BLQ or ALQ), then these will be displayed in the listings as ' $< xx$ ' or ' $> yy$ ', where xx and yy are the lower and upper limits respectively of detection or quantitation.

For estimated creatinine clearance, results > 60 will be displayed as ' > 60 '. Hence, estimated glomerular filtration rate (eGFR) will be calculated as:

The revised Schwartz estimate will be used:

$$\text{eGFR (mL/min)} = (36.2 \times \text{height}) / \text{serum creatinine},$$
 where height is measured in cm and serum creatinine is measured in $\mu\text{mol/L}.$

eGFR will be indexed to body surface area (BSA) using the following formula:

$$\text{eGFR (mL/min/1.73 m}^2\text{)} = \text{eGFR (mL/min)} \times 1.73/\text{BSA},$$
 where BSA is based on the Du Bois and Du Bois formula:

$$\text{weight } 0.425 \times \text{height } 0.725 \times 0.007184,$$

where weight is measured in kg and height is measured in cm.

When available, enzymatic serum creatinine will be used. Otherwise, the Jaffe serum creatinine will be used. If height or weight is missing at the collection date, then the closest value to the sample date will be used. If there is more than one height or weight value on the same day, or 2 height or weight values equally distant from the collection date, then the mean will be used.

Values will be categorized as 'Normal', 'Low' or 'High' based on normal range.

For serum creatinine values that are reported as BLQ, eGFR will be set to missing.

Treatment emergent ALT or AST is defined as criteria not met at baseline but met at any time post-baseline:

- Alanine aminotransferase (ALT) $> 1 \times \text{ULN}$ at baseline
- Aspartate aminotransferase (AST) $> 1 \times \text{ULN}$ at baseline
- ALT or AST $> 1 \times \text{ULN}$ at baseline
- Treatment emergent ALT $> 3 \times \text{ULN}$, $> 5 \times \text{ULN}$ and $> 8 \times \text{ULN}$

- Treatment emergent AST > 3×ULN, > 5×ULN and > 8×ULN
- Treatment emergent ALT or AST > 3×ULN, > 5×ULN and > 8×ULN
- Treatment emergent ALT or AST > 3×ULN and either bilirubin > 2×ULN or INR > 1.5

Participants who meet treatment-emergent ALT or AST criteria will be listed.

9.2.2 Urinalysis

Urinalysis results will be listed.

9.3 Vital Signs, Other Physical Findings and Other Safety Data

9.3.1 Vital Signs

Any relevant findings at screening are included as part of the participant's medical history. Any changes seen after screening that are indicative of an AE are to be recorded as such on the AE form and included as part of the AE listing.

Vital signs data will be listed for all participants in the safety analysis set. Vital signs data include blood pressure, body temperature, pulse rate, respiratory rate, head circumference and whether potentially clinically significant based on criteria presented APPENDIX 2.

9.3.2 Physical Examination

Physical examination data will be listed for all participants in the safety analysis set. Physical examination data include weight and height.

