### **3.5. Benefit/Risk Assessment**

Cannabidiol oral solution has been approved for use in treatment of seizures associated with LGS, DS, and TSC. [REDACTED]

[REDACTED]

Participants in the current study may experience some improvement of symptoms and will receive comprehensive clinical exams and clinical monitoring associated with the study. The risks of participation are primarily associated with adverse reactions to GWP42003-P, although there may also be some discomfort from collection of blood samples and other study procedures. Cannabidiol oral solution contains 79 mg/mL ethanol. In this study in young children, there may be a potential risk of accumulation when CBD-OS is chronically coadministered with other medicines containing ethanol or other substrates for alcohol dehydrogenase (such as propylene glycol). Clinical judgment should be used weigh potential benefit from CBD-OS against this potential risk. More information about the known and expected benefits, risks, and reasonably anticipated AEs associated with GWP42003-P may be found in the current approved version of the Investigator's Brochure (IB) (CBD-OS IB).

The most commonly reported side effects include somnolence; decreased appetite; diarrhoea; transaminase elevations; fatigue, malaise, and asthenia; rash; insomnia, sleep disorder, and poor-quality sleep; infections; pyrexia; and vomiting. Serious side effects include hepatocellular injury, somnolence and sedation, suicidal behaviour and ideation, and hypersensitivity reactions. Further information is included in the latest CBD-OS IB.

Overall, the extensive clinical safety and efficacy results of GWP42003-P were demonstrated across 5 Phase 3 studies, an open-label study, and the expanded access program in the treatment of paediatric epilepsy syndromes. And it is believed that GWP42003-P has a favourable benefit risk profile for the treatment of seizures associated with TSC, DS, and LGS in the participant age ranges being investigated in this study.

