#### 8.1.2. Dose Escalation and Dose Adjustments

The 52-week treatment period includes a fixed 2-week titration schedule followed by flexible dose optimisation. The optimal dose will be based on the participant's observed efficacy, safety, and tolerability per the investigator's clinical judgement.

On Day 1 (Visit 3) of treatment with GWP42003-P, participants will initiate the fixed 2-week titration of GWP42003-P, beginning with a dose of 5 mg/kg/day (2.5 mg/kg b.i.d.). On Day 8 ( $\pm$  3 days), the dose will be increased to the target dose level of 10 mg/kg/day (5 mg/kg b.i.d.). Participants will be observed on Day 15 (Visit 5).

After Day 15 (Visit 5), the GWP42003-P dose may be escalated further based on individual clinical response and tolerability using a flexible titration schedule, per the investigator's clinical judgement. If, in the investigator's opinion, the participant is experiencing a clinically meaningful improvement in seizures, investigators will have the option to maintain or increase a participant's dose at any time during or between scheduled visits until EOT. Doses may be increased up to a maximum of 20 mg/kg/day (10 mg/kg b.i.d.) for LGS and DS or 25 mg/kg/day (12.5 mg/kg b.i.d.) for TSC, in maximum weekly increments of 5 mg/kg/day ( $\leq$  2.5 mg/kg b.i.d.). If possible, changes in dose should be avoided during the 3 days prior to PK visits or before PK samples have been collected on the day of PK study visits (as specified in [APPENDIX 1](#)) unless clinically indicated for safety ([Section 9.1.10.1](#) provides additional details).

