#### **9.1.5. Physical Examination**

Physical examinations will include length (height), body weight, and head circumference measurements. A full physical examination will be completed at Visit 1; an abbreviated physical examination may be completed at each subsequent visit, as clinically indicated.

Any findings related to (neuro)developmental or growth issues considered to represent an AE must be documented on the eCRF.

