Visit Number	1	2 d	3 e	4 d	5	6 d	7	8 d	9	10	11 d , 12 d	13	14 d , 15 d	16	17 d , 18 d , 19 d	20	21	22 d	
Day	-2 8	-14	1	8	15	22	29	36	57	85	113 , 141	169	197, 225	253	281, 309, 337	365	375	403	
Window (days)	±3		+3		±3		±7												
																			
samples are collected.
 
 
In cases where participants are not able to attend study visits due to special circumstances (e.g., COVID-19 pandemic), the investigator will discuss with the sponsor potential mitigation approaches for
 

Schedule of Activities																			
Study Period Visit	Screening/ Baseline Period (4 weeks)	Treatment Period (52 weeks)															End of Taper b	Safety Follow-up c	Notes
		Fixed		Flexible Dose Optimisation															
Visit Number	1	2 d	3 e	4 d	5	6 d	7	8 d	9	10	11 d , 12 d	13	14 d , 15 d	16	17 d , 18 d , 19 d	20	21	22 d	
Day	-2 8	-14	1	8	15	22	29	36	57	85	113 , 141	169	197, 225	253	281, 309, 337	365	375	403	
Window (days)	±3		+3		±3		±7												
																			GWP42003- P dispensing, secure delivery, and collection.
Collect Study Intervention/ Compliance Review				X		X	X	X		X			X		X	X			

Schedule of Activities																			
Study Period Visit	Screening/ Baseline Period (4 weeks)	Treatment Period (52 weeks)															End of Taper b	Safety Follow-up c	Notes
		Fixed		Flexible Dose Optimisation															
Visit Number	1	2 d	3 e	4 d	5	6 d	7	8 d	9	10	11 d , 12 d	13	14 d , 15 d	16	17 d , 18 d , 19 d	20	21	22 d	
Day	-2 8	-14	1	8	15	22	29	36	57	85	113 , 141	169	197, 225	253	281, 309, 337	365	375	403	
Window (days)	±3		+3		±3		±7												
Safety and Tolerability																			
Physical Examination	X		X	X		X	X	X		X		X	X	X	X			
 
• Each visit: Height/ length, weight, and head circumference
 
• Visit 1: full physical examination
 
• Subsequent clinic visits: abbreviated physical examination (as needed/ clinically indicated)
 
	

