This statistical analysis plan (SAP) describes the planned analysis and reporting for Jazz Pharmaceuticals Research UK Limited “Jazz” protocol number GWEP17005 (An Open-label, Single-arm Study to Assess the Safety, Pharmacokinetics, and Efficacy of Adjunctive Cannabidiol Oral Solution (GWP42003-P) in Participants with Tuberous Sclerosis Complex (1 month to < 2 years of age), Dravet Syndrome (1 year to < 2 years of age), or Lennox-Gastaut Syndrome (1 year to < 2 years of age) who Experience Inadequately-controlled Seizures), dated 24-Jan-2024 version 6.0. Reference materials for this SAP include the protocol and the accompanying sample data collection documents. Operational aspects related to collection and timing of planned clinical assessments are not repeated in this SAP unless relevant to the planned analysis.

The structure and content of this SAP provides sufficient detail to meet the requirements identified by the Food and Drug Administration (FDA), European Medicines Agency (EMA), and International Conference on Harmonization (ICH) of Technical Requirements for Registration of Pharmaceuticals for Human Use: Guidance on Statistical Principles in Clinical Trials¹. All work planned and reported for this SAP will follow internationally accepted guidelines, published by the American Statistical Association² and the Royal Statistical Society³, for statistical practice.

The planned analyses identified in this SAP may be included in clinical study reports (CSRs), regulatory submissions, or future manuscripts.

The SAP described hereafter is *an a priori* plan. It will be submitted to file prior to any descriptive analysis of data pertaining to the Jazz Pharmaceuticals Research UK Limited “Jazz” (formerly GW) study GWEP17005.

In view of poor recruitment and retention, and the low likelihood of meeting planned enrollment, a decision was reached to terminate the study on 28 January 2025. Following database lock, an abbreviated CSR will be produced. This abbreviated SAP describes the analyses that will be undertaken to support CSR production.

2. Study Objectives and Endpoints

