APPENDIX 1 Abbreviations

Abbreviation	Definition
AE	Adverse Event
ALQ	Above the Limit of Quantification
ASM	Antiseizure Medication
BLQ	Below the Limit of Quantification
CBD	Cannabidiol
COVID-19	Coronavirus Disease 2019
CRO	Contract Research Organization
CSR	Clinical Study Report
D	Day
DS	Dravet Syndrome
ECG	Electrocardiogram
eCRF	Electronical Case Report Form
EDRS	Epilepsy Diary Reference Sheet
EEG	Electroencephalogram
ePRO	Electronic Participant Reported Outcome
EMA	European Medicines Agency
EOT	End of Treatment
ESCI	The Epilepsy Study Consortium
ET	Early Termination
FDA	Food and Drug Administration
ICF	Informed Consent Form
ICH	International Conference on Harmonisation
ILAE	International League Against Epilepsy
IMP	Investigational Medicinal Product
ITQOL-SF47	Infant Toddler Quality of Life Questionnaire – Short Form 47
LGS	Lennox-Gastaut Syndrome
MedDRA	Medical Dictionary for Regulatory Activities
PK	Pharmacokinetics
QTcB	QT-interval for ECG Corrected for Heart Rate Using Bazette's Formula
QTcB	QT-interval for ECG Corrected for Heart Rate Using Fridericia's Formula
RTSM	Randomization and Trial Supply Management
SAE	Serious Adverse Event
SAP	Statistical Analysis Plan
SD	Standard Deviation
SIF	Seizure Identification Form
SMC	Safety Monitoring Committee
SOC	System Organ Class
TEAE	Treatment-Emergent Adverse Event
TSC	Tuberous Sclerosis Complex
VEEG	Video Electroencephalogram
WHO	World Health Organization

APPENDIX 2 Ranges for Clinically Significant Changes and Other Defined Flagged Values in Vital Signs

The range of values that will be used to identify clinically significant changes in vital signs parameters (See Section 9.3.1) are presented in Table 3. Ranges for Potentially Clinically Significant Changes in Vital Signs.

Table 3. Ranges for Potentially Clinically Significant Changes in Vital Signs

Vital Sign	Range
Supine Systolic BP (mmHg)	Change: < -20, > 20
Supine Diastolic BP (mmHg)	Change: < -10, > 10
Pulse Rate (beats/min)	Change: < -10, > 10

Defined flagged values that will be used to identify low or high vital signs parameters (See Section 9.3.1) are presented in Table 4. Other Defined Flagged Values for Vital Signs

Table 4. Other Defined Flagged Values for Vital Signs

Vital Sign	Flag
Supine Systolic BP (mmHg)	< 70, > 121
Supine Diastolic BP (mmHg)	< 32, > 76
Pulse Rate (beats/min)	< 95, > 210
Temperature (°C)	> 38.0, < 35.5
Respiratory Rate (breath/min)	< 15, > 53

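### Weight, height and head circumference are listed only as measured values, and the head circumference flag has no criterion, so growth faltering not reported as an adverse event is hard to detect

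*SAP*

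**What the plan says.** **Collection.** Protocol Section 9.1.5 states: "Physical examinations will include length (height), body weight, and head circumference measurements". The note on physical examination in the Schedule of Activities asks for "Height/ length, weight, and head circumference" at each visit. Section 9.1.5 also requires growth findings that are considered adverse events to be documented.

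**Weight and height.** SAP Section 9.3.2 lists the data for the safety analysis set: "Physical examination data include weight and height".

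**Head circumference.** SAP Section 9.3.1 places it in the vital signs listing: "head circumference and whether potentially clinically significant based on criteria presented APPENDIX 2". Appendix 2 introduces its Table 3 as "The range of values that will be used to identify clinically significant changes in vital signs parameters".

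**Setting.** Protocol Section 8.1.2 says: "The 52-week treatment period includes a fixed 2-week titration schedule followed by flexible dose optimisation". Entry age is 1 month to under 2 years for TSC and 1 to under 2 years for DS and LGS. SAP Section 1 records that "a decision was reached to terminate the study on 28 January 2025" and that the SAP is an abbreviated one.

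**The concern.** All three measures increase with age in healthy children of this age. A listing of measured values therefore shows most children gaining, whether they follow their expected curve or drop away from it. There is no control arm, so age- and sex-expected growth is the natural comparator, and the plan does not use it.

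Slowed growth is a plausible harm here. Protocol Section 3.5 says: "The most commonly reported side effects include somnolence; decreased appetite; diarrhoea", and the same list includes vomiting. Efficacy is not evaluated in the abbreviated report (SAP Section 8), so safety and pharmacokinetics are most of what the study can still deliver.

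The head circumference flag is a separate and purely internal problem. The SAP promises an output for which it supplies no rule.

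**Working it through.** **1. Does Appendix 2 support the flag?**

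| Measure | Table 3 (change) | Table 4 (flagged value) |
|---|---|---|
| Systolic BP | yes | yes |
| Diastolic BP | yes | yes |
| Pulse rate | yes | yes |
| Temperature | no | yes |
| Respiratory rate | no | yes |
| Head circumference | no | no |
| Weight, height | no | no |

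Three parameters have change criteria and five have flagged values. Head circumference is in neither table.

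**2. Is growth standardised elsewhere?** No z-score, centile or growth velocity appears in either document. Body mass index is listed at baseline only (SAP Section 7.3.1). Protocol Section 13.7.1.3 plans summary statistics for physical examination data, without age standardisation.

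**3. How far can a child fall while still gaining?** The documents give no figure to reproduce, so this is an illustration on assumed inputs, none of which come from the documents:

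- G, expected weight gain over 52 weeks: 2.0 to 5.0 kg
- SD, reference standard deviation at follow-up: 1.0 to 1.3 kg
- f, fraction of the expected gain achieved: 0.25, 0.50, 0.75
- the child starts at the median (z = 0)

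Raw change = f × G. Change in z = −(1 − f) × G / SD.

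| f | Raw change (kg) | Smallest fall in z (G = 2.0, SD = 1.3) | Largest fall in z (G = 5.0, SD = 1.0) |
|---|---|---|---|
| 0.75 | +1.50 to +3.75 | 0.25 × 2.0 / 1.3 = 0.38 | 0.25 × 5.0 / 1.0 = 1.25 |
| 0.50 | +1.00 to +2.50 | 0.50 × 2.0 / 1.3 = 0.77 | 0.50 × 5.0 / 1.0 = 2.50 |
| 0.25 | +0.50 to +1.25 | 0.75 × 2.0 / 1.3 = 1.15 | 0.75 × 5.0 / 1.0 = 3.75 |

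At f = 0.50 the child moves from the 50th centile to between the 22nd and the 0.6th.

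Raw weight rises in every row by construction, because f is above zero. The useful question is how late the raw listing shows a plateau. That needs f = 0, by which point z has fallen by 2.0 / 1.3 = 1.54 to 5.0 / 1.0 = 5.00.

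**4. Shorter follow-up.** The study stopped early, so 52 weeks cannot be assumed for every child. Taking half of G for 26 weeks (even gain, same SD, both simplifications) gives G of 1.0 to 2.5 kg. At f = 0.50 the raw change is +0.50 to +1.25 kg and z falls by 0.5 × 1.0 / 1.3 = 0.38 to 0.5 × 2.5 / 1.0 = 1.25. The effect is smaller but the mechanism is the same.

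**The case against.** A reader might infer that no growth signal could be seen at all. The documents do not support that:

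- Growth findings considered adverse events must be documented (Protocol Section 9.1.5), and all adverse events are listed (SAP Section 9.1). Decreased appetite, diarrhoea and vomiting reported as adverse events would appear there too.
- The neurodevelopmental examination, which covers feeding concerns, is listed (Protocol Section 9.1.6, SAP Section 9.4).
- The ITQOL-SF47 item on satisfaction with physical growth is listed at baseline and end of treatment (SAP Section 8.2, Appendix 4).
- Age in months and gender are listed (SAP Section 7.3.1), so a reader could standardise each child by hand.

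A reader might also infer that every child was followed for a year, or that the SAP drops an analysis of growth against age that the protocol promised. Neither holds. The study was terminated early, and Protocol Section 13.7.1.3 specifies no age standardisation. The reduction to listings is declared in SAP Section 9.6 and is not itself an error. Nor do the documents say that these measurements are taken because growth is a concern; weight, for instance, also sets the dose volume.

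Two further points have force. Listing content is set in separate shells that are not available here, so derived growth columns cannot be ruled out. The Appendix 2 cross-reference may be only a drafting slip, meant for those parameters that do have criteria.

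These points narrow the concern without removing it. The adverse event route depends on investigator judgement with no stated threshold. The ITQOL-SF47 item records caregiver satisfaction, not measurement. Standardising by hand means working through each child and visit with no named reference. The listings-only design is no obstacle either, because the SAP already lists derived values: eGFR indexed to body surface area and treatment-emergent ALT/AST criteria (Section 9.2.1), and age-specific ITQOL-SF47 scores (Appendix 4).

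**Conclusion.** The point holds in a limited form. The SAP text provides growth data only as measured values, and the promised head circumference flag has no criterion. The second part is certain from the text alone. The consequence of the first is that growth faltering which an investigator does not report as an adverse event is hard to detect in the listings; it is not invisible.

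The size rests on assumed growth figures. On those, half the expected 52-week gain hides a fall of 0.77 to 2.50 z behind a raw gain of 1.0 to 2.5 kg, and less over shorter follow-up. A child who stops gaining or loses weight would show in the raw listing. The point concerns how the data are presented for safety review and does not undermine the study's conclusions. It is a cheap improvement.

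**What to change.** 1. In SAP Sections 9.3.1 and 9.3.2, create one growth listing with weight-for-age, length/height-for-age and head-circumference-for-age z-scores by sex, from a named published growth standard, beside the measured values. Show the change from baseline at each visit, using the Section 6.1.2 baseline definition.
2. State how age at measurement is obtained: from date of birth where available (Protocol Section 9.1.2 collects it, subject to local regulations), otherwise from age in months at consent (SAP Section 6.1.9.3 records age in months) carried forward by study day.
3. Mark falls beyond a threshold stated before the data are listed. This is a listing flag for analysis only, not a clinical rule.
4. Move head circumference to the growth listing, or remove it from the Appendix 2 flag sentence.

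**Cost.** A small amount of programming and one listing, on data already collected. Z-scores are imprecise in young infants, especially if only age in months is available. Without a control arm they cannot separate a drug effect from disease, feeding problems or other antiseizure medication, so flagged falls would be prompts for review and not evidence of causation.

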9.3.3 ECG

ECG data will be listed for all participants in the safety analysis set. ECG data include mean heart rate, RR interval, PR interval, QRS duration, QT interval, QTcB and QTcF and whether potentially clinically significant based on criteria given in APPENDIX 3.

9.4 Comprehensive Neurodevelopmental Assessments

Neurodevelopmental assessments will be performed at Visits 3, 13, and EOT and will include recording of the following aspects:

- Paediatric neurological examination
- Developmental milestones assessment
- Recording of ongoing health conditions such as seizures, changes in participant's health (e.g., AEs), changes in concomitant medications, including use of rescue medications
- Longitudinal monitoring of neurodevelopment via Clinician Global Impression of Change/Severity (CGIC/CGIS) for sensory, motor, cognition, emotional/behavioral health, communication, social, and adaptive functioning

- Quality of life assessments via Infant and Toddler Quality of Life Questionnaire Short Form 47 (ITQOL-47)

CGIC/CGIS will be listed for all participants in the safety analysis set, which will include assessments at the following domains: sensory, motor, cognition, emotional/behavioral health, communication, social and adaptive functioning.

Comprehensive neurodevelopmental exam will be listed for all participants in the safety analysis set.

